6.4.1.3 Missing Observations for the AOBP SBP

For general guidance about the missing values, see 6.2.7. Guidance on handling the missing observations is provided below.

Table 6 Missing observations imputation for the primary efficacy estimand

Cause for Missing Observation	Type of Missingness	Imputation Approach	Rationale
Lack of follow-up observation in subject with ICE ID #1.	MNAR	Values for the missing observation will be imputed using the distribution for the subjects with ICE ID#1 who do not miss the value (so called “retrieved dropouts”), within the same randomized sequence, if such approach is possible. In case there are not enough retrieved dropouts within the same sequence, the imputation will be performed by Jump to the Reference Group (Placebo Arm)	Retrieved dropouts’ imputation is closest to following a treatment strategy for missing observations. Jump to reference as a last resort is conservative imputation strategy that disfavors treatment effect.
Death for any cause (ICE Event #2)	MNAR	This observation is missing by default. The endpoint will be imputed to assign a poor outcome value by applying a distribution of the worst 5% of the observations across both randomized sequences.	The treatment policy strategy is not applicable as there are no post-event observations. Death, as an unfavorable truncating event prevents observations to be obtained.
Premature study discontinuation in subjects without ICE (e.g. loss to follow-up, withdrawal of consent)	MAR	Values for the missing observations will be imputed using the randomized sequence specific distribution	These observations are assumed to be missing at random and will be imputed as a part of the treatment arm they belong to.

Cause for Missing Observation	Type of Missingness	Imputation Approach	Rationale
Missing observation due to failure to obtain AOBP in subjects without ICE	MAR	Values for the missing observations will be imputed using the randomized sequence specific distribution	AOBP may fail for technical reasons or subject may miss the visit. These observations are assumed to be missing at random and will be imputed as a part of the treatment arm they belong to.

6.4.1.4 Primary Efficacy Estimation

The primary analysis of the primary efficacy estimand will assess the superiority of lorundrostat 25 mg QD dose compared to placebo in mean change in AOBP SBP from TP baseline (TP1 Baseline and TP2 Baseline) to TP Week 4 (TP1 Week 4 and TP2 Week4).

The analysis includes two baselines (TP1 baseline and TP2 baseline). The primary analysis will be based on the work of Mehrotra DV, 2014 and Jemielita, T., et al. 2016. Specifically, the Model IV from Mehrotra DV, 2014 will be used for the primary analysis as the best performing model for pairwise correlation of 0.6 and balanced 2x2 design. Sensitivity analyses will use additional models as specified later.

Example of SAS code for the planned estimation is provided below. The actual code may differ from the example depending on the data, carry-over effect and convergence.

```
proc mixed data = file;  
class trtseqp aperiodc trtp usubjid;  
model aval = xdiff trtseqp aperiodc xdiff*aperiodc trtp ;  
repeated aperiodc/subject=usubjid(trtseqp) type=un;  
estimate 'Lorundrostat v placebo' trtp 1 -1 /cl alpha=0.1;  
lsmeans trtp /pdiff cl alpha=0.1;
```

where,
trtseqp is a planned treatment sequence (Lorundrostat-Placebo and Placebo-Lorundrostat),
aperiodc is analysis period (TP1 and TP2),
trtp is planned treatment (Lorundrostat and Placebo),
xdiff is a difference between TP1 baseline and TP2 baseline.

The estimate statement depends upon the coding of the variables and needs to be adjusted accordingly.

6.4.1.5 Sensitivity analysis

Sensitivity analyses will be performed as follows:

[figure not shown]

[figure not shown]
[figure not shown]

[figure not shown]
[figure not shown]
[figure not shown]

[figure not shown]

- Using observed data only,
- Assuming that all missing values are MAR
- Utilizing a longitudinal linear analysis model as described in Cheng X, et al., 2021

6.4.1.6 Subgroup analyses for Primary Efficacy

[REDACTED]

6.4.2 Exploratory Efficacy Endpoint Analyses

    
	

   
	
  

   
	
  

   
	
  

[REDACTED]		[REDACTED]	[REDACTED]	
[REDACTED]		[REDACTED]	[REDACTED]	
[REDACTED]		[REDACTED]	[REDACTED]	
[REDACTED]		[REDACTED]	[REDACTED]	
[REDACTED]		[REDACTED]	[REDACTED]	

6.5 Pharmacokinetic Evaluations

[REDACTED]

6.6 Safety Evaluations

6.6.1 Safety Treatments Displays

Safety analyses will be conducted using the Safety Analysis Set. All safety events starting or worsening of the existing AE between the first dose in the TP1 and the First dose in the TP2 (Week 0 to Week 8, including the washout) will be allocated to the medication received first in the randomized sequence (lorundrostat or placebo). All AEs starting or worsening of the existing AE from the first dose in the Treatment Period 2 to the End of Treatment / End of Study, whichever is later, will be allocated to the medication starting in the TP2 (lorundrostat or placebo).

All AE Summary displays will present AEs by Treatment Period and Treatment Group within the period and, by Treatment Group Total.

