While the existing class of MRAs address the “aldosterone breakthrough”, the new ASI class has the potential for a more favorable benefit/risk profile due to the differentiated mechanism of action, which results in a decrease in circulating and local aldosterone production, rather than the marked increase seen with the MRA class. Lorundrostat, a selective ASI, is an inhibitor of cytochrome P450 11B2 (CYP11B2; aldosterone synthase), which is a rate-limiting enzyme for aldosterone production. The results of a series of pharmacology studies demonstrate that lorundrostat is a selective inhibitor of CYP11B2 and is not associated with adverse effects upon the central nervous, respiratory, or cardiovascular systems. Unlike spironolactone, the most commonly prescribed MRA, and other ASIs in development, lorundrostat, because of its short half-life, has the potential to be rapidly reversible should AEs such as hyperkalemia or hypotension be encountered. Data from both a Phase 1 study in healthy subjects (NCT02953132) and a Phase 2 study in patients with uncontrolled hypertension, Target-HTN (NCT05001945), have shown lorundrostat to have acceptable safety profile and be well tolerated.

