9.1 Analysis Sets

The intent-to-treat (ITT) analysis set includes all subjects, regardless of whether treatment was received.

The full analysis set (FAS) will include all subjects who receive at least one dose of study drug. Subjects will be categorized according to the treatment assignment.

The safety analysis set (SAF) will include all subjects who receive at least one dose of study drug. Subjects will be categorized according to the treatment received in the respective study periods.

The population pharmacokinetics (popPK) analysis set will include all subjects who received at least one dose of lorundrostat and had at least one evaluable popPK sample taken. Subjects in this analysis set will be categorized according to the treatment received.

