2.1 Introduction

This is a randomized, double-blind (DB), placebo controlled, crossover study with a two-period, two-sequence (2x2) design evaluating the efficacy and safety of 25 mg QD lorundrostat (an aldosterone synthase inhibitor (ASI)) in addition to a SGLT2i for the treatment of hypertension in subjects with CKD and albuminuria despite receiving stable treatment with an ACEi or an ARB. Subjects will be at least 18 years old with hypertension (Automated office blood pressure (AOBP) SBP [REDACTED] inclusive at Randomization), and mild to severe CKD (eGFR

██████████ with albuminuria (UACR ██████████ inclusive) at the Screening Visit.

Approximately 60 subjects will be enrolled in approximately 30-40 investigational centers in the US.

The expected duration of the study for each subject from Screening to the End of Study visit is expected to be approximately 18 weeks: consisting of a 2-week screening period, a 2-week run-in period where subjects will either begin study provided dapagliflozin 10 mg or continue on their regularly prescribed SGLT2i, and two double blind (DB) 4-week treatment periods separated by a 4-week washout period:

* Either study provided commercially available dapagliflozin 10mg QD or continue regularly prescribed SGLT2i

**End of Study: Subjects who do not participate in the OLE, will attend a 2week End of Study Safety Followup visit.

Abbreviations: OLE, open label extension; QD, once daily SGLT2i, sodium glucose cotransporter2 inhibitor

Subjects will be randomized (1:1) to two treatment sequences: lorundrostat-placebo (LP) and placebo-lorundrostat (PL).

Treatment allocation will be organized as follows:

- Treatment Period 1 (DB Study Week 0 to Study Week 4): Subjects will receive a lorundrostat 25 mg (sequence LP) or one matching lorundrostat-placebo tablet (sequence PL) dosed orally QD.
- Washout (Study Week 4 to Study Week 8): All subjects will receive matching placebo dosed orally QD.
- Treatment Period 2 (DB Study Week 8 to Study Week 12): Subjects will receive one matching lorundrostat-placebo tablet (sequence LP) or a lorundrostat 25 mg (sequence PL) dosed orally QD.

During the DB and Washout periods, subjects will continue their background therapy including ACEi/ARB and SGLT2i.

If at any time during the DB periods, eGFR drops by $\geq 30\%$ from Randomization, a decision on dose reduction, dose hold or dose withdrawal/discontinuation will be made in consultation between the Investigator and the Medical Monitor.

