5.2 Data Conventions

Subjects

Screened subject is any subject who signs informed consent.

Screen Failure is any subject that does not get randomized, regardless of inclusion/exclusion criteria status.

Randomized Subject is any subject that receives Randomization ID in eCRF.

Study Arms

Randomized Sequence refers to the sequence to which the subject was randomized. There are two randomized sequences (Lorundrostat-Placebo and Placebo-Lorundrostat). If the reference is made to the as Randomized Arm, it is the same as sequence.

Treatment Arm refers to lorundrostat and placebo. Each subject is planned to receive both lorundrostat and placebo treatment, in prespecified order as defined by the sequence.

Study day

Efficacy analysis will consider study day relative to the date of the first exposure to the treatment. Any events and observations on or after the date of the first exposure to the treatment will be calculated as: assessment date – date of the first exposure to the treatment + 1. As such, the date of the first exposure to the treatment is study day 1. For any events before the date of the first exposure to the treatment, study day will be calculated as: assessment date – date of the first exposure to the treatment

Period and date definitions

Screening Period: Period prior to Run-in Period (Week -2). The screening period starts on the day of enrollment (signing of the informed consent).

Run-In: The period from enrollment into Run-in Period to Randomization Visit (Week 0)

Last Run-In dose date will be the last dose date of administered Dapagliflozin or their regularly prescribed SGLT2i prior to randomization.

Treatment Period 1 (TP1): A double-blind period from Randomization to last dose (study treatment) date of TP1 or Study Week 4 Date, whichever is later.

Washout Period: A single-blind placebo period from after the end of TP1 to before first investigational administration of Treatment Period 2 (TP2) or Study week 8 visit, whichever is later.

First Washout dose date will be the first dose date of placebo after last investigational drug administration during TP1.

Last Washout dose date will be the last dose date of placebo prior to first investigational drug administration during TP2.

Treatment Period 2 (TP2): A double-blind period from first investigational drug administration during TP2 or Study Week 8 visit, whichever is later, to last investigational drug administration or Study week 12 / EoT visit, whichever is later.

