6.6.2.6 AE Displays

An overall AE summary will be presented by the number and percent of subjects with one or more events of specific type and total number of events of specific type by Treatment Period, Treatment Group within Treatment Period and Treatment Group in Total with the following:

- TEAEs
- TEAEs by worst severity (mild/moderate/severe)
- Treatment-related TEAEs
- Treatment-related TEAEs by worst severity (mild/moderate/severe)
- Serious AEs (SAEs)

- Treatment Emergent SAEs
- Treatment-related Treatment-emergent SAEs
- Adverse Events of Special Interest (AESIs)
- TEAEs leading to permanent discontinuation of study investigational drug
- TEAEs leading to dose modification of the investigational drug
- AEs with death as an outcome
- TEAEs with death as an outcome
- Treatment-related AEs with death as an outcome

The following AE summaries will be produced by MedDRA SOC and PT with the counts and percent of subjects with one or more event and counts of events for each PT and SOC level. The outputs will be presented by the alphabetic order of SOC and PT classes. The summary will be by Treatment Period, Treatment Group within Treatment Period and Treatment Group in Total.

- Any AE
- AEs in Run-In Period
- TEAEs
- TEAEs by worst severity (mild/moderate/severe)
- Treatment-related TEAEs
- Treatment-related TEAEs by worst severity (mild/moderate/severe)
- Serious AEs (SAEs)
- Treatment Emergent SAEs
- Treatment-related Treatment -emergent SAEs
- Adverse Events of Special Interest (AESIs)
- TEAEs leading to permanent discontinuation of study investigational drug
- TEAEs leading to dose modification of the investigational drug
- AEs with death as an outcome
- TEAEs with death as an outcome

The following AE listings will be prepared:

- AEs in Run-In Period
- TEAEs
- TEAEs by worst severity (mild/moderate/severe)

- Treatment-related TEAEs
- Treatment-related TEAEs by worst severity (mild/moderate/severe)
- Serious AEs (SAEs)
- Treatment Emergent SAEs
- Treatment-related Treatment -emergent SAEs
- Adverse Events of Special Interest (AESIs)
- TEAEs leading to permanent discontinuation of study investigational drug
- TEAEs leading to dose modification of the investigational drug
- AEs with death as an outcome
- TEAEs with death as an outcome

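### Adverse events starting in the 4-week placebo washout are tabulated under the Period 1 drug, and no planned AE summary shows washout or follow-up onset separately

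*SAP*

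**What the plan says.** SAP 6.6.1 sets the allocation rule for safety events. For onset or worsening between the first dose of Treatment Period 1 and the first dose of Treatment Period 2, the rule is: "Week 0 to Week 8, including the washout) will be allocated to the medication received first in the randomized sequence". Events "from the first dose in the Treatment Period 2 to the End of Treatment / End of Study, whichever is later" go to the second drug. SAP 6.6.2.2 counts washout events as treatment-emergent, and follow-up events too if they occur within 14 days of the start of follow-up.

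Dosing covers only part of those windows. SAP 2.1 gives "Treatment Period 1 (DB Study Week 0 to Study Week 4" for Period 1, followed by "Washout (Study Week 4 to Study Week 8): All subjects will receive matching placebo dosed orally QD". SAP 5.2 defines the washout as a period of its own: "A single-blind placebo period from after the end of TP1 to before first investigational administration".

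SAP 6.6.2.6 presents AE summaries by "Treatment Period, Treatment Group within Treatment Period and Treatment Group in Total". Run-in events have their own definition (SAP 6.6.2.1) and their own table; washout events have neither.

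On reversibility, Protocol 2.2 says that lorundrostat, "because of its short half-life, has the potential to be rapidly reversible should AEs such as hyperkalemia or hypotension be encountered". Protocol 4.2 relies on reversibility of blood pressure and the 4-week washout to keep carryover small.

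**The concern.** The safety tables are meant to show what happens on lorundrostat compared with placebo. Under SAP 6.6.1, the Period 1 lorundrostat column holds four weeks on drug and four weeks on placebo. If the drug wears off as quickly as the protocol expects, the second four weeks add mostly background events.

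There are two consequences. First, background events are added under both treatment labels, which pulls ratios of event rates towards 1. Second, single events can carry a label that does not match what the subject was taking. Subjects may enter with systolic pressure up to 180 mmHg (Protocol 5.1), and a reading above 180 mmHg is an adverse event of special interest (AESI; SAP 3.3). If an LP subject's pressure rises after lorundrostat is stopped and exceeds 180 mmHg at Week 8 before the Period 2 dose, the event counts under lorundrostat after four weeks of placebo. Every AE, SAE and AESI summary by treatment inherits this rule.

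**Working it through.** **Inputs.** Screening 2 weeks, run-in 2, Period 1 4, washout 4, Period 2 4 (SAP 2.1). EoS visit 2 weeks after the last dose, only for subjects who do not enter the extension (SAP 2.1). About 60 subjects randomized 1:1 (SAP 2.2), so 30 per sequence. The share f of subjects who attend EoS is not given; the range 0 to 1 is used.

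**The plan's own figure.** 2 + 2 + 4 + 4 + 4 + 2 = 18 weeks, which matches the stated duration of approximately 18 weeks. The Period 1 attribution window is 4 + 4 = 8 weeks, which matches Week 0 to Week 8. The documents give no figure for the off-drug share.

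**Time labelled lorundrostat, per LP and PL (placebo-lorundrostat) pair.** LP contributes 8 weeks and PL contributes 4 + 2f, in total 12 + 2f. On drug: 4 + 4 = 8. Off drug: 4 + 2f.

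- f = 0: off drug 4/12 = 33.3%, or 120 of 360 patient-weeks. All of it is washout.
- f = 1: off drug 6/14 = 42.9%, or 180 of 420 patient-weeks. Washout alone is 4/14 = 28.6%.
- Within the Period 1 lorundrostat column: 4/8 = 50%. Within the Period 2 column: 0% (f = 0) to 2/6 = 33% (f = 1).

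**Time labelled placebo.** PL contributes 8 weeks and LP contributes 4 + 2f, again 12 + 2f. The pooled windows are equal.

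**Dropout (assumed 10% to 20%, leaving at Week 4 or Week 8).** The lowest share is 20% leaving at Week 4 with f = 0: 3.2/10.4 = 31%. The highest is 20% leaving at Week 8 with f = 1: 5.6/12.8 = 44%.

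**Effect on a rate ratio.** Assume constant rates and excess risk only during dosing. The apparent ratio is (8 × RR + 4 + 2f)/(12 + 2f).

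- RR = 2.0: 20/12 = 1.67 (f = 0); 22/14 = 1.57 (f = 1).
- RR = 3.0: 28/12 = 2.33; 30/14 = 2.14.
- RR = 0.5: 8/12 = 0.67; 10/14 = 0.71.

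**Effect on the percentage of subjects with an event.** Assume a 5% background risk per four weeks and a hazard ratio of 2 during dosing.

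- On treatment only: lorundrostat 1 − 0.95² = 9.75%, placebo 5.00%. Difference 4.75 points, ratio 1.95.
- SAP rule, f = 0: lorundrostat is the mean of 1 − 0.95³ = 14.26% and 9.75%, so 12.01%. Placebo is the mean of 9.75% and 5.00%, so 7.38%. Difference 4.63 points, ratio 1.63.
- SAP rule, f = 1: lorundrostat is the mean of 14.26% and 1 − 0.95^2.5 = 12.04%, so 13.15%. Placebo is the mean of 9.75% and 1 − 0.95^1.5 = 7.41%, so 8.58%. Difference 4.57 points, ratio 1.53.

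At a 20% background risk the same steps give differences of 16.0 points on treatment, and 14.4 (f = 0) to 13.6 (f = 1) under the SAP rule. Ratios shrink clearly in every case; differences shrink noticeably only when background risk is high.

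**The case against.** The case for the present rule is substantial, and most of it stands.

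- Charging washout events to the preceding drug is a recognised way to catch delayed and withdrawal effects. The protocol says only that the drug has the potential to be rapidly reversible, and it plans a check for carryover. Findings at Week 4 are also followed up during the washout. This is a good reason to keep the rule.
- The SAP plans counts and percentages of subjects for AEs, not rate ratios. On the risk-difference scale the dilution is small at low background risk.
- Only one scheduled visit, Week 8, observes the washout. If an event type is detected only at scheduled visits, the lorundrostat-labelled visits are Weeks 2, 4 and 8 in LP and Weeks 10 and 12 in PL, plus Week 14 with EoS. On-drug visits are then 4/5 = 80% or 4/6 = 67%. A ratio of 2.0 would appear as 1.80 to 1.67, and 0.5 as 0.60 to 0.67.
- Laboratory values are summarized by analysis visit (SAP 6.6.3.2), so Week 4 and Week 8 can be compared there. Five of the eight AESIs require a change or stop of study drug, so an equal background rate in the washout is untested for them.

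Three stronger readings are tempting, but the documents do not support them. A reader might infer that the 8-week window loads extra exposure onto lorundrostat; it does not, because placebo has the same window in the other sequence. A reader might infer that on-drug and off-drug events can no longer be told apart; SAP 5.2 defines the dose dates and SAP 6.6.2.6 plans listings, so they can. A reader might see a breach of Protocol 9.1, which says of the safety set: "Subjects will be categorized according to the treatment received in the respective study periods". That sentence classifies subjects and gives no rule for events with onset in the washout, so a conflict is not established.

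None of this supplies the missing summary. Under the planned tables, an event arising on placebo in LP appears only as a lorundrostat event.

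**Conclusion.** The point holds as a gap in presentation. Between 33% and 43% of the time labelled lorundrostat is off drug, of which washout accounts for 29% to 33% of labelled time and post-Period 2 follow-up for the rest. It would be wrong to attribute the whole range to the washout.

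The shares assume 60 completers in balanced sequences; the assumed dropout widens them to 31% to 44%. The apparent rate ratio of 1.67 to 1.57 for a true 2.0 also assumes constant rates and no excess risk after the last dose. If the drug has delayed or withdrawal effects, the dilution is smaller and the present rule captures something real.

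The safety objective can still be answered, and the comparison is not tilted by exposure time. What the planned tables cannot show is how much of each treatment's event count arose on that treatment. This is a low-cost improvement, not a fault that invalidates the safety analysis.

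**What to change.** Keep the Week 0 to Week 8 allocation. Add to SAP 6.6.1 and 6.6.2.6 an on-treatment summary of TEAEs, SAEs and AESIs, counting onset or worsening from the first to the last dose of each treatment period plus one short lag stated in advance. In the same table set, show washout-onset and follow-up-onset events in separate columns by preceding treatment (after lorundrostat, after placebo). Where the lag overlaps the start of washout or follow-up, say in which column such events are counted, so that none is counted twice.

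The cost is SAP wording and one extra table set from onset and dose dates already collected. There are two drawbacks. The lag is a judgement, which the retained tables offset. The finer split also relies more on AE start dates imputed under SAP 6.6.2.4, so a footnote should give the number of events placed by an imputed date.

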6.6.2 Adverse Events

Adverse events definitions are provided in the protocol.

6.6.2.1 AEs during the Run-In Period

Any AEs occurring after the first dose of SGL2-i medication in the Run in Period and before the first dose of the investigational medication (lorundrostat/placebo) in the DB period are considered AEs in the Run-In period. This definition also includes worsening of the existing AE during the Run-In period.

